4.2. Scientific Rationale for Study Design

This is an open label, randomized, balanced, three treatment, three period, three sequence, single dose, crossover study to evaluate the bioequivalence of test Griseofulvin tablets, 500 mg versus reference Griseofulvin tablets, 500 mg as well as dose proportionality of test Griseofulvin tablets, 250 mg and 500 mg, in healthy, adult participants under fed conditions.

GSK will manufacture new GRISOVIN 500mg as well as 250mg products with SLS enhanced new formulations for better absorption. In the view of same, a three-period cross-over design was selected so that within participant comparisons can be utilized. Three-way crossover study with Test GRISOVIN 250 mg, GRISOVIN 500 mg and Reference GRISOVIN 500 (ASPEN) is selected along with Dose normalization – where GRISOVIN 250 mg single dose is given and the results are multiplied by 2.

The Pharmacokinetic (PK) sampling and washout period are designed to ensure that PK parameters are well-estimated and pre-dose concentrations are completely negligible in subsequent periods.

Sampling time points were decided based on the pharmacokinetic parameters of Griseofulvin in past successful global BE study¹⁵ and the pharmacokinetic data available in SPC⁶. The last sampling time point was selected as 96 hours (> 3 half-lives) considering the elimination half-life of around 9.5 hrs – 21 hours. The study is planned in fed condition as the SPC^{6, 15} of griseofulvin recommends it's intake with food. BE study conforms to CDSCO and/or other global regulatory guidelines.

4.3. Justification for Dose

Griseofulvin is indicated in the treatment of fungal infections of the skin, scalp, hair or nails caused by *Microsporum spp.*, *Trichophyton spp.*, *Epidermophyton spp.*, where topical therapy is considered inappropriate or has failed.

Approved dose of Griseofulvin in adults (greater than or equal to 50 kg) is 500 to 1,000 mg daily, but not less than 10 mg/kg bodyweight daily. A single daily dose is often satisfactory, but divided doses may be more effective in patients who respond poorly. Griseofulvin is recommended with 500 mg twice a day dose to manage the dermatophytosis in the current scenario. Griseofulvin 1000 mg/ day dose is needed for the treatment of infections that are more difficult to eradicate, such as tinea pedis. Hence,

Griseofulvin 500 mg tablet twice a day dose will be useful for patients requiring 1000 mg daily dose. The test product (T1) is a tablet containing 500 mg of Griseofulvin and it will be compared with the reference product (Griseofulvin 500 mg tablet) to demonstrate bio-equivalence. The safety of Griseofulvin Tablets, 500 mg when given as a single dose, in healthy volunteers is established through different studies. As per the literature¹⁵ a single oral dose of 500 mg results in quantifiable levels of Griseofulvin.

The test product T2 containing Griseofulvin 250 mg is indicated in patients requiring 250 mg Griseofulvin tablet twice a day (500 mg daily dose). The present study involves administration of test product T2 containing 250 mg Griseofulvin to evaluate its dose proportionality with 500 mg tablet.

Both 250mg and 500mg are approved doses in India, and Australia.

The dosing of each treatment will be done under fed condition based on the recommendation given in the SPC^{6, 15} to take the drug after meal, to increase the rate and extent of absorption.

4.4. End of Study Definition

A participant is considered to have completed the study if he/she has completed all periods of the study including post study evaluation.

The end of the study is defined as the date of last scheduled procedure shown in the Schedule of Activities.

5. STUDY POPULATION

Prospective approval of protocol deviations to recruitment and enrolment criteria, also known as protocol waivers or exemptions, is not permitted.

5.1. Inclusion Criteria

Participants are eligible to be included in the study only if all of the following criteria apply:

Age

1. Participant must be 18 to 45 years of age inclusive, at the time of signing the informed consent.

Type of Participant and Disease Characteristics

2. Participants who are healthy as determined by the investigator or medically qualified designee on a medical evaluation including medical baseline history, physical

examination and vital sign examination (blood pressure, pulse rate, respiration rate and body temperature).

3. Participants with clinically acceptable findings as determined by haematology, biochemistry, urinalysis, 12 lead ECG.
4. Participant's willingness to follow the protocol requirements especially abstaining from xanthine containing food or beverages (chocolates, tea, coffee or cola drinks) or grapefruit or grapefruit juice, any alcoholic products, the use of cigarettes and the use of tobacco products from 48.00 hours before the start of dosing until after collection of the final pharmacokinetic (PK) sample and adherence to food, fluid and posture restrictions.
5. Participants with no history of significant alcoholism (Volunteers who do not have habit of heavy drinking which is defined as regular intake of more than 2 units of alcohol per day for male and 1 unit for female {1 unit= 150 ml of wine or 360 ml of beer or 45ml of 40% of alcohol}).
6. Participants with no history of drug abuse (benzodiazepines and barbiturates) for the last one month and other illegal drugs (*Appendix 2*) for the last 06 months.
7. Participants who are non-smokers and ex-smokers will be included. "Ex-smokers are someone who completely stopped smoking for at least 3 months."

Weight

8. Body mass index (BMI) within the range 18.5-30 kg/m² (inclusive) and weight ≥ 50 kg.

Sex

9. Healthy Male and non-pregnant female

Contraceptive use by men or women should be consistent with local regulations regarding the methods of contraception for those participating in clinical studies.

a. Male Participants:

Male participants are eligible to participate if they agree to the following during the treatment period and for at least six months after the last dose of study treatment:

- Refrain from donating sperm as well as agree to use contraception/barrier as detailed below
 - Agree to use a male condom and should also be advised for a female partner to use a highly effective method of contraception as a condom may break or leak when having sexual intercourse with a woman of childbearing potential who is not currently pregnant
 - Agree to use male condom when engaging in any activity that allows for passage of ejaculate to another person

b. Female Participants:

- A female participant is eligible to participate if she is not pregnant and intending to become pregnant or breastfeeding, and at least one of the following conditions applies:
 - Is not a woman of childbearing potential (WOCBP)
OR
 - Is a WOCBP and using a contraceptive method that is highly effective, with a failure rate of <1%, as described in [Appendix 4](#) during the treatment period and for at least 1 month after the last dose of study treatment. The investigator should evaluate the effectiveness of the contraceptive method in relationship to the first dose of study treatment.
 - A WOCBP must have a negative highly sensitive [[Appendix 2](#)] pregnancy test (serum as required by local regulations) within 1 day before each dose of study treatment (The participant must be excluded from participation if the serum pregnancy result is positive).
- Additional requirements for pregnancy testing during and after study treatment are located in [Appendix 2](#).
- The investigator is responsible for review of medical history, menstrual history, and recent sexual activity to decrease the risk for inclusion of a woman with an early undetected pregnancy

Informed Consent

10. Capable of giving signed informed consent as described in [Appendix 1](#) which includes compliance with the requirements and restrictions listed in the informed consent form (ICF) and in this protocol.

5.2. Exclusion Criteria

Participants are excluded from the study if any of the following criteria apply:

Medical Conditions

1. Known history of hypersensitivity to Griseofulvin.
2. Participants who have taken prescription medications or over-the-counter products (including vitamins, minerals and/or herbal supplements) within 14 days prior to administration of IMP.
3. Any medical or surgical conditions, which might significantly interfere with the functioning of gastrointestinal tract, blood-forming organs etc.

4. History of cardiovascular, renal, hepatic, ophthalmic, pulmonary, neurological, metabolic, haematological, gastrointestinal, endocrine, immunological or psychiatric diseases.
5. History of malignancy (including skin cancers) or other serious diseases.
6. History of porphyria.
7. Known history of SLE (Systemic lupus erythematosus) in the exclusion criteria.

Prior/Concomitant Therapy

8. Participants consuming aspirin, oral contraceptive pills, phenobarbital, and warfarin having potential to trigger drug interactions with griseofulvin for any ailment in the previous 28 days, prior to dosing day.

Prior/Concurrent Clinical Study Experience

9. Participation in a clinical drug study or bioequivalence study 90 days prior to period I dosing of the present study.

Diagnostic assessments

10. Participants with positive HIV tests, HBsAg or Hepatitis-C tests.
11. Found positive in breath alcohol test.
12. Found positive in urine test for drug abuse.

Other Exclusions

13. Blood donation 90 days prior to period I dosing of the present study.
14. History of problem in swallowing pills.
15. Any contraindication to blood sampling i.e. keloid formation.
16. Sensitivity to heparin or heparin-induced thrombocytopenia.
17. Premenarchal female subjects

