2. INTRODUCTION

2.1. Study Rationale

This is an open label, randomized, balanced, three treatment, three period, three sequence, single dose, crossover study to evaluate the bioequivalence of test Griseofulvin tablets, 500 mg versus reference Griseofulvin tablets, 500 mg as well as dose proportionality of test Griseofulvin tablets, 250 mg and 500 mg, in healthy, adult participants under fed conditions.

GSK will manufacture new GRISOVIN 500mg as well as 250mg products with SLS enhanced new formulations for better absorption. In the view of same, a three-period cross-over design was selected so that within participant comparisons can be utilized. Three-way crossover study with Test GRISOVIN 250 mg, GRISOVIN 500 mg and Reference GRISOVIN 500 (ASPEN) is selected along with Dose normalization – where GRISOVIN 250 mg single dose is given and the results are multiplied by 2.

The Pharmacokinetic (PK) sampling and washout period are designed to ensure that PK parameters are well-estimated and pre-dose concentrations are completely negligible in subsequent periods.

Sampling time points were decided based on the pharmacokinetic parameters of Griseofulvin in past successful global BE study¹⁵, the pharmacokinetic data available in SPC⁶ and previously conducted studies by Accutest. The last sampling time point was selected as 96 hours (> 3 half-lives) considering the elimination half-life of around 9.5 hrs – 21 hours. The study is planned in fed condition as the SPC^{6, 15} of griseofulvin recommends it's intake with food.

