2.3.1. Risk Assessment

Potential Risk of Clinical Significance	Summary of Data/Rationale for Risk	Mitigation Strategy
Investigational Product (IP) [Griseofulvin Tablets]		
Concurrent treatment with oral contraceptives	Concurrent treatment with griseofulvin may reduce the effectiveness of oral contraceptives, so additional non-hormonal contraceptive precautions should be taken during griseofulvin treatment and for a month after stopping griseofulvin.	As per inclusion criteria (Section 5.1), participants will be included if they agree to follow the contraceptive guidance described in Appendix 4 .
Photosensitivity reaction	Since a photosensitivity reaction is occasionally associated with griseofulvin therapy, patients should be warned to avoid exposure to intense natural or artificial sunlight.	As per the study requirement, participants will be housed in clinical facility up to 24.00 hours post dose and thereafter will be advised to avoid exposure to intense natural or artificial sunlight until completion of 5 days post last dose.
Allergic reaction	Hypersensitivity to any ingredient of the preparation	The participants will be closely monitored by medical personnel for occurrence of any allergic reaction. Appropriate medication required to treat allergic reaction will be kept ready.

Carcinogenicity and Mutagenicity
	
Long-term administration of griseofulvin with food has been reported to induce hepatomas in mice and thyroid tumours in rats but not in hamsters. The clinical significance of these findings in man is not known. In view of these data, griseofulvin should not be used prophylactically.⁷
 
Griseofulvin was mentioned in the report of a cohort study designed to screen 215 drugs for carcinogenicity. Although an excess of thyroid cancer was reported among users of griseofulvin in a 9-year follow-up, no results for this drug were reported in a 15-year follow-up, implying that no significant association was observed for cancer.¹⁷
	
Being a single dose study this risk can be considered as negligible.

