
Interaction with Other Drugs
	
Barbiturates may reduce the effectiveness of griseofulvin by interference with the gastrointestinal absorption of griseofulvin. The concurrent use of substances such as phenylbutazone and sedative and hypnotic drugs which induce metabolizing enzymes should be avoided as the blood level, and hence efficacy, of griseofulvin may be reduced.
 
Griseofulvin may decrease the response to coumarin anticoagulants administered concomitantly. Dosage adjustment of the anticoagulant may be required during therapy and after griseofulvin therapy.
 
Patients should be warned that an enhancement of the effects of alcohol by griseofulvin has been reported.
	
This is a single dose study in healthy Participants where in Griseofulvin will be given for PK evaluation and not for efficacy evaluation. The Participants included in the study will already be free of prescription medications or over-the-counter (OTC) products (including vitamins and minerals) within 14 days prior to administration of study treatment. Moreover, participants taking enzyme modifying drugs will not be allowed to participate. All Participants will be advised not to take any medicine during the entire period of study to avoid PK interaction.
 
As per inclusion criteria (Section 5.1), participants with no history of significant alcoholism will be included. Participation also requires the subject's willingness to abstaining from any alcoholic products from 48.00 hours before the start of dosing until after collection of the final pharmacokinetic (PK) sample.

--	---	---

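### Exclusion 1 screens for hypersensitivity to griseofulvin only, although the protocol's own risk table names any ingredient of the preparation and both test tablets are new SLS-enhanced formulations

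*Protocol*

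**What the plan says.** **Hypersensitivity.** Exclusion 1 in Protocol 5.2 reads "Known history of hypersensitivity to Griseofulvin". The allergic-reaction row of the risk table (2.3.1) gives the risk as "Hypersensitivity to any ingredient of the preparation". Its mitigation is that "The participants will be closely monitored by medical personnel for occurrence of any allergic reaction", with medication to treat a reaction kept ready. On the products, 2.1 says that "GSK will manufacture new GRISOVIN 500mg as well as 250mg products with SLS enhanced new formulations for better absorption", and 4.2 repeats this. SAP 2.3 confirms that each participant is to receive all three treatments.

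**Enzyme-modifying drugs.** The interaction row of the same table says that volunteers will be "free of prescription medications or over-the-counter (OTC) products (including vitamins and minerals) within 14 days prior to administration of study treatment", and then: "Moreover, participants taking enzyme modifying drugs will not be allowed to participate". In 5.2, exclusion 2 bars all prescription and over-the-counter products, herbal supplements included, for 14 days before dosing. Exclusion 8 applies a 28-day look-back to a short list: "Participants consuming aspirin, oral contraceptive pills, phenobarbital, and warfarin having potential to trigger drug interactions with griseofulvin". Section 6.5 repeats the 14-day abstention but allows an exception where the investigator and sponsor judge that a medication will not interfere.

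**The concern.** The risk table identifies a hazard, and the eligibility criteria screen for only part of it. The missing part is the one most specific to this study. The benefit/risk argument in 2.3 and 2.3.3 rests on griseofulvin being a long-marketed drug, which says little about the other ingredients of two new tablets. A known allergy can be found by asking before the first dose; monitoring begins to help only once the tablet has been swallowed. Section 2.3.2 states that participants gain no direct benefit, so an avoidable exposure has nothing to offset it. Sections 5 and 8 prohibit waivers, so sites will work from the text of 5.2 rather than from the risk table.

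A lesser matter is that 2.3.1, 5.2 and 6.5 describe the handling of enzyme-modifying drugs in three different ways.

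**Working it through.** No arithmetic applies to the main point, and the plan states no figure to reproduce. The check compares the risk table with every criterion in 5.1 and 5.2.

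**Step 1. Could any criterion other than exclusion 1 cover a tablet ingredient?**

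| Criterion | What it covers | Closes the gap? |
|---|---|---|
| Inclusion 2 | Healthy in the investigator's judgement | Only by discretion |
| Exclusion 3 | Conditions interfering with the gut, blood-forming organs and the like | No |
| Exclusion 4 | History of disease by organ system, including immunological | Does not name allergy or ingredient hypersensitivity |
| Exclusion 16 | "Sensitivity to heparin or heparin-induced thrombocytopenia" | No; heparin is used in sampling and is not listed as part of the tablets |

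None does. Exclusion 16 shows that the authors did write a specific sensitivity criterion for a substance used in sampling, but they wrote none for the tablets beyond griseofulvin itself.

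**Step 2. How do the other rows of the risk table mitigate?** The contraceptive, pregnancy, male-participant and alcohol entries all point to criteria in 5.1. The allergy row points to none. It relies on monitoring and ready medication.

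**Step 3. Who is exposed?** At most 36 participants are randomised, and each is to receive T1, T2 and R. The documents contain no ingredient list and do not say whether R contains SLS, so the difference in ingredients between products cannot be described further.

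**Step 4. Is the bar on enzyme-modifying drugs implemented?**
- The bar is in the present tense: it concerns participants who are taking such drugs. It gives no look-back and follows directly on the 14-day statement.
- Exclusion 2 removes anyone who took any medicine in those 14 days, which includes every current user of an enzyme-modifying medicine.
- Inclusion 6 (no benzodiazepine or barbiturate abuse in the last month) and exclusion 12 (urine screen, with both classes on the Appendix 2 panel) add some cover.
- Exclusion 8 uses 28 days and names phenobarbital, but does not name the class.
- Section 6.5 contains an opinion-based exception that exclusion 2 lacks.

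The bar is therefore met through exclusion 2. What remains is that the sections do not say the same thing.

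**The case against.** **On hypersensitivity.** The risk table never promises an exclusion. It promises monitoring with treatment at hand, so no stated commitment is broken. The investigator judges health from the medical history, takes history again at each check-in, and may withdraw a participant for safety (7.2). No allergy signal for any ingredient is described. All of this is correct and limits the size of the point. It does not remove it: discretion is weaker than a criterion, and withdrawal after a reaction comes after the exposure that a screening question could have prevented.

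**On enzyme-modifying drugs.** A reader might infer that the bar has no counterpart in 5.2. Exclusion 2 shows otherwise. A reader might also subtract 14 days from 28, conclude that drugs stopped 15 to 28 days before dosing leave a gap, and argue that fading enzyme induction would add within-participant noise to both primary comparisons. The documents do not support this:
- Nothing in them says that induction lasts more than 14 days after stopping.
- The interaction row describes barbiturates as interfering with absorption, and coumarins as drugs whose response griseofulvin may reduce. Neither statement concerns lingering induction.
- Exclusion 8 is a list of interacting drugs. A longer window for a few named drugs does not contradict a general 14-day rule.

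For the same reasons the documents give no basis for extending the 28-day window to a whole drug class.

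**Conclusion.** The point on exclusion 1 stands. The criterion is narrower than the risk the protocol itself names, nothing else in Section 5 closes the difference, and the test tablets are new formulations. It is a gap between a named risk and the criteria, and it concerns participant safety. It has no bearing on sample size, power or the primary analyses. In scope it covers every ingredient except griseofulvin. In numbers it is probably very small, but the documents allow no estimate. The conclusion assumes that sites apply 5.2 as written, which the ban on waivers supports.

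The enzyme-modifier wording is a secondary matter of reconciliation. The documents show neither a missing exclusion for current users nor any effect on the bioequivalence or dose-proportionality results.

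**What to change.** Extend exclusion 1 to known hypersensitivity to griseofulvin or to any ingredient of the administered products (T1, T2, R), and cite the criterion in the allergy row of 2.3.1 beside the existing monitoring. Sites would need the ingredient lists to ask the question. The check fits into the medical history already scheduled at screening. The cost is one phrase and, at most, an occasional extra screen failure.

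Separately, the sponsor should reconcile 2.3.1, exclusions 2 and 8 in 5.2, and the exception in 6.5, so that the handling of enzyme-modifying drugs is stated once and consistently. Which drugs and which window apply is for the sponsor to decide. No change to the SAP is needed.

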5.3. Lifestyle Considerations

5.3.1. Meals and Dietary Restrictions

- Refrain from consumption of grapefruit or grapefruit juice, pomelos, exotic citrus fruits, grapefruit hybrids, or fruit juices from 48.00 hours before the start of dosing until after collection of the final pharmacokinetic (PK) sample.
- In each study period, all participants will be required to fast overnight for at least 10.00 hours prior to receiving high-fat and high-calorie breakfast. After dosing the participants will not be allowed food for at least 04.00 hours. Meal timings are summarized in the SoA.

- On dosing study days, after an overnight fast of 10.00 hours, all participants will be given the same high-fat and high-calorie breakfast, 30 min prior to drug administration. Participants should eat the high-fat and high-calorie breakfast completely within 25 minutes.
- No water is allowed for 01.00 hour before the start of dosing until 01.00 hour after dosing except 240 ± 2 mL of water administered to the participants for dosing of study treatments. Water is allowed ad libitum at all other times.

5.3.2. Caffeine, Alcohol, and Tobacco

- During each dosing session, participants will abstain from ingesting caffeine- or xanthine-containing products (e.g., coffee, tea, cola drinks, and chocolate) for 48.00 hours before the start of dosing until after collection of the final pharmacokinetic (PK) sample.
- During each dosing session, participants will abstain from alcohol for 48.00 hours before the start of dosing until after collection of the final PK sample.
- Use of tobacco products will not be allowed for 48.00 hours before the start of dosing until after collection of the final pharmacokinetic (PK) sample.

